Members of the research team proposing this work have developed and tested a successful model of lifestyle education for use in India (D-CLIP, Diabetes Community Lifestyle Improvement Program²⁵) and have conducted many studies in India and elsewhere which have shown positive health effects of improving diet quality.²⁶⁻⁴⁰ Building on this research, we propose implementing and evaluating the acceptability, delivery, effectiveness, and cost-effectiveness of a worksite-based lifestyle improvement package: a peer-led lifestyle change program with group-based classes on weight loss/maintenance, dietary improvements and increasing physical activity delivered in worksite environments that facilitate these changes (for example, by offering healthy food options in the canteen). Since the evidence unequivocally shows that lifestyle change is efficacious and essential for diabetes prevention and management and is already part of authoritative guidelines⁴¹ and given that this is an implementation trial that could result in the subsequent scale-up of efforts, we propose using a pre-post trial design to assess if the intervention package can prevent diabetes and cardiovascular disease risk factors in adults with prediabetes (HbA_{1c} of 5.7-6.4%) or unmedicated diabetes (HbA_{1c} ≥ 6.5%, but currently not taking diabetes medications) in India. Among 2000 people with prediabetes or early diabetes identified from eight diverse worksites in India with stakeholder commitment, we will use a mixed methods approach to evaluate a worksite-based, culturally tailored intervention package. The study aims:

Aim 1: To measure the success of implementation and inform the scalability of this intervention program by evaluating: (a) *program adoption* by assessing participation and changes in weight and diet and physical activity behaviors among lifestyle class participants; (b) *fidelity to the program* by assessing activities of study-affiliated worksite staff; changes to the food options at the worksite canteen; management support for the program; and changes in the worksite environment; and (c) *acceptability of the program* through (i) in-depth, semi-structured interviews with study site management and employees and lifestyle education program dropouts and (ii) focus group discussions with lifestyle education program participants.

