Aim 2: To measure the effectiveness of the program among participants by evaluating the change in number of individuals reaching two or more of cardiometabolic risk goals, namely reductions in blood pressure, triglycerides, and HbA_{1c} (the primary outcome), and through changes in secondary outcomes including rates of diabetes incidence and regression to normoglycemia and changes in anthropometry, lipids, and fasting glucose.

Aim 3: To measure the value and return on investment of the intervention for employers by assessing program cost and cost-effectiveness and changes in staff productivity, absenteeism, health status, and quality of life.

If the program is shown to be feasible, acceptable, effective, and cost-effective at these worksites, the results of this study will be used to make recommendations and dissemination plans on how to implement and sustain lifestyle interventions at worksites to improve the health of workers and communities for other sites within these companies, other Indian worksites, organizations involved in promoting worksite wellness and/or chronic disease prevention, and to India's National Programme for Prevention and Control of Diabetes, Cardiovascular Diseases, and Stroke. Furthermore, lessons from this study can be used to make recommendations or plan studies of similar worksite programs in the U.S. and other settings outside of India.

Significance

The Diabetes Epidemic: Type 2 diabetes mellitus (T2DM) is an economically costly disease and a major cause of morbidity and mortality globally.^{4,42} Eighty percent of the 382 million people worldwide with diabetes live in low- and middle-income countries.¹ Asian Indians living worldwide are particularly susceptible to developing T2DM, with high prevalences of T2DM and T2DM risk factors (e.g., beta-cell dysfunction, central adiposity), higher rates of progression from prediabetes to diabetes,⁴³ and lifestyles that pre-dispose to T2DM (e.g., high-fat, low fiber diets and low physical activity).^{2,44-46} Asian Indians fare worse than several other populations after developing T2DM (poor glycemic control, higher rates of complications).⁴⁷⁻⁵⁰

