Table 1: Demographic Overview of Study Sites

Company name	Location	Type of Industry	Number of Employees	Employee Age-range	Percent Women
Chennai Petroleum Corporation Ltd	Chennai	Oil Refinery	1,500	30-55	1-2%
L&T Infotech	Chennai	Technology and Business Services	3-5,000	20-50	30-35%
Cognizant Technology Solutions	Chennai	Technology and Business Services	50,000	25-55	30-40%
Rourkela Steel Plant	Rourkela	Mining and Steel Manufacturing	18,000	19-65	26%
TATA Consultancy Services	Chennai	Technology and Business Services	50,000	25-55	30-40%
Bokaro Steel Plant	Bokaro	Mining and Steel Manufacturing	19,000	19-65	31%
Bhilai Steel Plant	Bhilai	Mining and Steel Manufacturing	30,000	19-65	27%
TATA Steel	Jamshedpur	Mining and Steel Manufacturing	36,418	19-65	29%

Study Sample: Inclusion criteria are: aged ≥ 18 years; overweight or obese using World Health Organization defined South-Asian cut-points: BMI ≥ 23 kg/m² and/or waist circumference ≥ 90 cm for men and ≥ 80 cm for women;⁷⁵ have prediabetes (HbA_{1c} of 5.7-6.4%) or diabetes (HbA_{1c} $\geq 6.5\%$); not currently taking any diabetes medications; not pregnant or breastfeeding; and without history of heart disease, current serious illness, or conditions which would impede participation in an unsupervised physical activity and diet change program.

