Preliminary data: D-CLIP [clinicaltrials.gov #NCT01283308, Emory University and Madras Diabetes Research Foundation (MDRF) investigators] is an on-going, translational, diabetes prevention study comparing standard lifestyle advice to a step-wise, culturally tailored program (group lifestyle classes plus metformin for participants not responding to lifestyle change alone) among 602 people with prediabetes in India.²⁵ D-CLIP was developed based on the DPP Curriculum.^{79,80} Early unpublished D-CLIP results are promising. The participation rate for intervention classes was high (83%), and loss to follow-up was low (9%). At eighteen months, lifestyle participants had significantly greater reductions in weight (-1.7 vs. -0.8 kg), BMI (-0.6 vs. -0.3 kg/m²), and waist circumference (-2.7 vs. -2.0 cm) than controls. Additionally, intervention participants showed greater improvements in systolic blood pressure, triglycerides, and HbA_{1c}; 21% of controls achieved improvement in two or more of these risk factors while 33% of intervention group did so. Similar to previous studies showing that weight, BMI, and waist circumference reductions significantly predicted diabetes risk reduction in lifestyle interventions,⁸¹ preliminary D-CLIP analyses show a 51% relative risk reduction in diabetes incidence in intervention participants compared to controls. The effects of the D-CLIP intervention were consistent across sex, age, income, education, and baseline BMI and glucose intolerance.⁸²

Recommendations for improving the Indian diet to better prevent diabetes and reduce cardiometabolic risk factors will be developed based on the work assessing the value of improving food quality of the Global Nutrition and Epidemiologic Transition (GNET) initiative at Harvard University and MDRF. For example, a small crossover trial of substituting brown rice for white rice for five days, found that brown rice lowered glucose levels by 19.8% and fasting insulin by 57%.⁴⁰ GNET studies in other populations further support benefits of improving carbohydrate quality.³⁸ Moreover, studies of acceptability of brown rice in India indicate that well-informed, sensory trained panelists readily accepted brown rice,³² but translating this intervention to the public

Figure 2: Components of the Lifestyle Intervention at the Individual and Worksite Environment Levels

will require additional education and training.²⁷

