Aim 2: Statistical analysis of intervention impact: A generalizing estimating equations (GEE) framework for clustered data⁹⁷ will be used to assess the statistical significance of any observed intervention effect on the endpoints. For the primary endpoint, the dependent variable will be the indicator for whether the study participant is at two or more cardiometabolic risk factor reduction goals at the end of the 3 year follow-up period, minus the expected probability of this endpoint in the absence of an intervention, to be taken as 21% as observed in the D-CLIP²⁵ control group. An exchangeable working correlation matrix will be used to incorporate the clustering within the 8 work-sites, with a log link and binomial variance specified. The exponentiated point and interval estimates from the intercept of this model will quantify the intervention effect, and the p-value associated with the model's intercept will provide a measure of the statistical significance of the findings. A similar GEE approach will be used to estimate and test the significance of intervention effects on secondary endpoints. For continuous markers, such as systolic blood pressure and HbA_{1c}, the post- to pre- within-participant difference will serve as the dependent variable in a GEE model as above, with the identity link function and the distribution specified as normal. The change scores will be evaluated for outliers, and analysis will be repeated with and without extreme outliers. For the cumulative incidence of diabetes at end of follow-up, participants will be coded as one if they satisfy the diabetes definition at end of follow-up and 0 otherwise. A Cox proportional hazards regression model for the diabetes incidence rate will also be considered, and if dropout or loss to follow-up are non-negligible, causal methods for adjusting for dependent censoring will be applied.¹⁰² A similar approach will be used to assess regression to normoglycemia. We will consider worksite-level covariates in multi-level models to examine how these aspects might affect findings. Additional secondary endpoints will be considered (e.g., changes in being at 1, 2 and 3 CVD/T2DM risk factor goals). Although the study is not powered to detect it unless quite large and although no effect modification is expected, we will assess the presence of effect modification by calculating intervention effect estimates stratified by potential modifiers, such as gender, age, marital status, socio-economic status, and assess the statistical significance of any effect modification observed by calculating a cross-product term between the potential modifier and the intervention, using a robust score test to assess the significance of

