Sample Size Selection: This worksite-clustered before-after design of 8 worksites with at least 250 eligible and enrolled participants per site and no more than 20% loss to follow-up (LTF) after 3 years will have 93% or more power to detect an estimated difference between the percent of participants at 2 or more CHD risk factor goals after 3 years of follow-up, the primary effectiveness endpoint of this trial, of 33% or greater, compared to the comparable D-CLIP²⁵ percentage of 21%. The 20% 3-year LTF rate is likely conservative, as only 9% of D-CLIP participants have been lost to follow-up after a mean of 30 months. Similarly, the D-CLIP comparative percentage of 21% is likely conservative, because the D-CLIP control group also experienced a minimal intervention that included meeting with a physician and a dietician, attending two classes (a lecture on diabetes

prevention through weight loss and diet change, and an exercise class), and receiving handouts reinforcing prevention of T2DM. Thus, compared to a community control receiving none of these services, the D-CLIP group would be expected to have a higher percentage at or exceeding two goals, compared to the community standard. In addition, power in this study is excellent for numerous secondary effectiveness endpoints of considerable interest, including 90% power or more to detect a decrease of 2mmHg or greater in systolic blood pressure ($p=0.10$, IIS), 95% power or more to detect a decrease in HbA_{1c} of 0.14% or greater ($p=0.10$, IIS), and nearly 100% power to detect a reduction in diabetes incidence of 30% or greater among the 2/3 of the study participants with prediabetes at baseline screening, compared to the baseline rate of 0.07/year,¹²⁴ otherwise under the same assumptions as the primary endpoint calculation.

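### Diabetes incidence, a secondary outcome, is coded from final-visit status alone, which gives a prevalence and misses cases first met at earlier annual visits

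*Combined protocol and SAP*

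**What the plan says.** All references are to the combined protocol and SAP.

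- **Specific Aims, Aim 2** lists "changes in secondary outcomes including rates of diabetes incidence and regression to normoglycemia" as secondary outcomes.
- **Data Analysis, Aim 2** calls the diabetes outcome a cumulative incidence at end of follow-up. It gives this coding: "participants will be coded as one if they satisfy the diabetes definition at end of follow-up and 0 otherwise". It adds: "A Cox proportional hazards regression model for the diabetes incidence rate will also be considered". If dropout is not negligible, methods for dependent censoring are to be applied. For the reverse transition: "A similar approach will be used to assess regression to normoglycemia".
- **Sample Size Selection** powers a 30% lower diabetes incidence "among the 2/3 of the study participants with prediabetes at baseline screening, compared to the baseline rate of 0.07/year".
- **Specific Aims** and **Study Sample** admit people with HbA1c of 6.5% or more as well as people with prediabetes. Medication is a separate condition: "but currently not taking diabetes medications" in the first, "not currently taking any diabetes medications" in the second.
- **Data Collection, Table 4** schedules HbA1c, fasting glucose and medication use (type and dosage) at baseline, annually and at the end of follow-up.

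**The concern.** Cumulative incidence counts everyone at risk who has met the definition by a given time. The coding rule counts those who meet it at that time. The two differ whenever someone crosses the threshold and later reads below it, whether through treatment, behaviour change or measurement variation.

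Three things are missing from the analysis text:

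1. **Earlier cases.** Nothing carries forward a case first met at year 1 or 2, although the annual readings will exist.
2. **At-risk set.** The rule speaks of participants in general. The restriction to baseline prediabetes appears only in the power statement, so the quantity powered is not the quantity coded.
3. **Treatment.** The diabetes definition is not spelled out for follow-up, and no rule says how someone who has started a glucose-lowering drug is coded. Under the similar approach for regression to normoglycemia, a medicated participant could count as a success.

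The design has no control group. The result must therefore be read against an outside rate, and the only diabetes rate in the documents is 0.07/year. With no concurrent arm coded the same way, a coding artefact does not cancel. An apparent fall in new diabetes could come from the coding and not from the program.

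**Working it through.** **Inputs from the plan (Sample Size Selection).** 8 sites × 250 = 2,000 enrolled; 2/3 with prediabetes; 20% lost over three years; reference rate 0.07/year; target reduction 30%, so 0.07 × 0.7 = 0.049/year.

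**Assumptions.** Constant rate, visits at years 1, 2 and 3, and loss unrelated to outcome.

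**Participants at risk with a final visit.** 2,000 × 2/3 × 0.8 = 1,067.

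**The plan's own figure.** Three-year risks are p0 = 1 − exp(−0.21) = 0.1894 and p1 = 1 − exp(−0.147) = 0.1367.

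- Standard errors: √(0.1894 × 0.8106 / 1,067) = 0.0120 under p0, and √(0.1367 × 0.8633 / 1,067) = 0.0105 under p1.
- One-sample, two-sided 5% test: z = (0.0527 − 1.96 × 0.0120) / 0.0105 ≈ 2.78, giving power of 99.7%.

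This matches the stated power of nearly 100%, with participants treated as independent. Clustering would lower it, which is a separate matter. The figure rests on onset in the prediabetes set, not on final-visit status.

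**Timing of cases at 0.07/year.**

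| By year | Risk 1 − exp(−0.07t) | Cases among 1,067 |
|---|---|---|
| 2 | 0.1306 | 139 |
| 3 | 0.1894 | 202 |

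The share arising by year 2 is 0.1306 / 0.1894 = 0.690. The other 63 cases (31%) arise after year 2 and can first be seen at the final visit.

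**Effect of the coding.** Let s be the share of the year-1 and year-2 cases that read below the threshold at year 3. The documents do not give s. The end-status proportion is 0.1894 × (1 − 0.690 × s).

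| Assumed s | Cases dropped (139.4 × s) | Coded proportion | Apparent reduction in risk |
|---|---|---|---|
| 0 | 0 | 18.9% | 0 |
| 15% | 21 | 17.0% | 10% |
| 30% | 42 | 15.0% | 21% |
| 40.3% | 56 | 13.7% | 28% |

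The last row is solved for, not assumed. A 30% lower rate lowers three-year risk by 1 − 0.1367 / 0.1894 = 0.278, and 0.278 / 0.690 = 0.403. So if about 40% of earlier cases read below the threshold at the end, the coding would show the whole planned effect with no change in onset.

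**The case against.** **The at-risk set is named.** It is, for power, so it would be too strong to say that the plan has none. A reader might go further and infer that people enrolled with diabetes will be counted as new cases. The documents do not show that: the outcome is called incidence, and its power statement excludes them. What stands is that the analysis rule does not repeat the restriction.

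**Treated cases need not be coded 0.** This is fair. The entry text treats medication as something separate from having diabetes, so a treated person could still satisfy the definition. A reader might infer certain miscoding, but the follow-up definition is not given, so miscoding is only possible. The opposite rule, that any drug start is an event, cannot be assumed either: the predecessor trial, D-CLIP, used "group lifestyle classes plus metformin for participants not responding to lifestyle change alone" in people with prediabetes.

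**A Cox model is on the page.** It would need first-event times and a risk set. But it is optional, and it has no event definition or dating rule. The dropout methods address censoring and non-adherence, not what counts as a case.

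**An external comparator is foreseen.** The closing section suggests using a longitudinal cohort for comparison. That is a complementary activity awaiting separate funding, and no coding rule is given for it.

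**The sizes are assumed.** They are. Only 18.9%, 202, 139 and 69% follow from the plan's figures plus a constant rate.

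**First occurrence has its own error.** This stands: single readings near the threshold produce false first crossings, and annual testing gives several chances for one.

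**Conclusion.** The point holds as a mismatch between label and rule. The plan names cumulative incidence and specifies final-visit prevalence, without counting earlier cases, restating the at-risk set or giving a treatment rule. At the plan's own rate, about 139 of 202 expected cases (69%) are exposed. The shifts to 17.0% and 15.0%, and the 40% needed to imitate the planned effect, are illustrations that depend on a share the documents do not give.

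A reader might infer that the coding necessarily flatters the program. That goes too far. Among participants with baseline prediabetes and a final visit, the end-status count cannot exceed the observed first-occurrence count. Against true onset, however, measurement noise at the final visit can add false cases, and failing to exclude baseline diabetes would push the figure up. The overall direction is not fixed.

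The outcome is secondary, and the primary endpoint is not affected.

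**What to change.** In Data Analysis, Aim 2:

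1. Restrict diabetes incidence to participants with prediabetes at baseline, as Sample Size Selection does.
2. Replace the end-status code with the first meeting of the diabetes definition at any annual visit, carried forward. Analyse it as discrete or interval-censored time to event, with censoring at the last attended visit and the plan's allowance for worksite clustering kept.
3. State the outcome definition (tests and thresholds) and how participants who start glucose-lowering drugs are coded, using the medication data already collected.
4. Report final-visit status separately by baseline group, labelled as prevalence.
5. Report regression to normoglycemia with and without participants on glucose-lowering medication.

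Give an event confirmed at two consecutive visits as a sensitivity analysis only. By construction it cannot confirm the roughly 63 cases first seen at the final visit, and it misses anyone who reverts before the next visit, so it should not be read against 18.9%.

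**Cost.** A few sentences of text and some recoding, with no new visits. The apparent benefit may be smaller. Because single-reading first occurrence can overcount, show it beside the confirmed and final-visit figures. The recoding does not make 0.07/year a like-for-like comparator: by its title, the cited source concerns impaired glucose tolerance, whereas this trial enrols on HbA1c.

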The program evaluation will use mixed methods techniques to assess program acceptability, impact, and effectiveness. Although the goal of the program is to benefit employees, the program evaluation includes measures such as cost-effectiveness, changes in employee absenteeism/presenteeism and qualitative assessments of employee views of the program that will be beneficial to employers using or considering this program for their worksite. In addition, the acceptability and impact of the program will be measured from the perspective of multiple stakeholders – program users, employees at the worksite, and worksite management. Understanding the program outcomes and acceptability from these multiple perspectives will provide rich data for making recommendations for sustaining and disseminating the program.

Although this study will be conducted in India, the results will be applicable to workers in other settings, including the U.S. (see Foreign Justification). Asians, including Asian Indians, are the fastest growing ethnic group in the U.S., and between 2000 and 2010 the Asian Indian population increased by 67.6%.⁷¹ Furthermore, several of the companies committed to this trial (the TATA group, L&T, and Cognizant) have locations worldwide, including offices in America, and these sites would be ideal locations for first phase dissemination. In addition, lessons learned in this study would benefit U.S. companies with worksites in India.

Approach

This study will use a pre-post design at eight diverse worksites to assess program implementation, fidelity, effectiveness, and impact on study participants, workers, and the worksite. There will be no control group because there is already convincing evidence from randomized trials^{8,9,17,53,58,72} that lifestyle intervention is beneficial for preventing diabetes and diabetes-related complications. Although randomized controlled trials provide the most robust evidence for effectiveness, meta-analyses have shown that the results of non-randomized, effectiveness studies do not systematically differ from the results given by randomized controlled trials of the same treatment.^{73,74}

Intervention

The lifestyle intervention will be conducted at eight worksites (see Table 1). These worksites have large workforces (1,500-50,000 employees) and represent a range of industries with locations across India. An overview of activities to be conducted at each worksite are shown in Figure 1.

[figure not shown]

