Quantitative data collection (Table 4) will occur at study-testing visits at baseline and every twelve months after lifestyle classes begin. Whenever possible, validated study instruments will be used. The primary outcome assessing program effectiveness (Aim 2) will be a composite of achieving two or more cardiometabolic risk goals; participants will be scored on the number of risk factors they improve on (0-3) with success delineated by a HbA_{1c} decrease $\geq 0.5\%$; a systolic blood pressure decrease ≥ 5 mm Hg; and a decrease in plasma triglycerides ≥ 10 mg/dl. This outcome was selected for three reasons: other risk scores for CVD (e.g., the Framingham Risk Score) do not perform as well in South Asian populations;⁹³ these risk factors are commonly measured by clinicians, so the results are clinically appropriate; and the composite outcome allows for individual variation in risk factor profiles and the ability of individuals to reduce different factors (e.g., an individual with a baseline HbA_{1c} of 5.8% is unlikely to reduce this risk factor by 0.5%, but may succeed in reducing triglycerides or blood pressure).

Table 4: Quantitative Data Collection Tools

Variable of interest (test)	Outcome of test	Timing			
		S	B	A	FU
Demographics and Lifestyle Behaviors					
Demographics (SQ)	Describe study population	X	X		
History of smoking (SQ)	Smoking status and cessation rates		X	X	X
Global Physical Activity Questionnaire (GPAQ) ⁹⁴	Baseline and changes in physical activity		X	X	X
Dietary intake (food frequency questionnaire)	Study specific food frequency questionnaire on dietary intake of foods targeted in the intervention		X	X	X
Dietary behaviors (SQ)	Prevalence of diet-related behaviors (e.g., reading nutrition		X	X	X

Variable of interest (test)	Outcome of test	Timing			
		S	B	A	FU
Weight loss history (SQ)	labels, eating at restaurants, measuring portions, etc.) Weight loss history including number and success of past attempts, methods used, etc.		X		
Quality of life (EQ-5D)	Baseline and changes in quality of life		X	X	X
Self-reported health (SF-12 and SQ)	Health status, recent health events and medication use (type and dosage of all prescription and over the counter medications and herbal remedies)		X	X	X
Worker satisfaction (SQ)	Questions assessing worker satisfaction with worksite, number of days missed work, self-described levels of productivity		X	X	X
Health-related outcomes					

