be modeled using generalized estimating equations for clustered, repeated measures data,⁹⁷ and heterogeneity in the intervention effect over time on each outcome by education, income, gender, age, baseline BMI category (normal weight, overweight, and obese), baseline physical activity, and baseline diet score will be evaluated.

- b) Program Fidelity: Program fidelity will be determined by measuring study-affiliated activities by the health education team, study canteen, and worksite management, changes in the worksite environment, and management support for the program. Checklists will be created for each study class and between-class activities (e.g., reviewing food and activity records, interactions with participants) to gather self-reported fidelity by health educators. Reasons for non-compliance will be assessed during monthly calls with the health education teams. To assess compliance to recommendations to provide healthy food options in the canteen, twice per year a member of the study team not affiliated with the worksite will do a random audit of available canteen foods and daily canteen menus will be collected and analyzed to determine amounts of and changes in number and types of healthy foods offered. In-depth interviews with employees (both program participants and non-participants) and managers/supervisors will be conducted to assess changes made at the worksite during the program.
- c) Program acceptability: We will assess program acceptability through in-depth, semi-structured interviews with managers and supervisors at the study sites, lifestyle program dropouts, and employees at the worksite (both program participants and ineligible/uninterested employees) and through FGD with program participants. Qualitative data will be supplemented by multiple choice and yes/no questions included on participant questionnaires asking about specific components of the lifestyle intervention (e.g., “How often do you choose brown rice instead of white rice?” or “Do you keep diet records?”). Percent reporting various answers and comparisons of percentages will be calculated.

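### With no control arm, the planned modifier-by-intervention test on the primary endpoint cannot separate effect modification from differences in background success

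*Combined protocol and SAP*

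**What the plan says.** The Approach section sets out a one-arm pre-post design: "There will be no control group because there is already convincing evidence".

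Under Data Analysis, Aim 2, the primary endpoint is an indicator of reaching at least two of three risk-factor goals at three years, "minus the expected probability of this endpoint in the absence of an intervention, to be taken as 21" percent, the figure seen in the D-CLIP control group. The effect is read from the constant term: "The exponentiated point and interval estimates from the intercept of this model will quantify the intervention effect". The model has no intervention variable that differs between participants.

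The same paragraph then plans effect estimates within strata (gender, age, marital status and socio-economic status are given as examples) and a formal test by "calculating a cross-product term between the potential modifier and the intervention, using a robust score test". No stratum-specific benchmark is given. The plan adds that it does not anticipate any modification and that power would be adequate only if modification were large.

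**The concern.** An interaction between a modifier and the intervention needs participants with and without the intervention, or some other contrast that stands in for it. The primary endpoint has neither. All participants are exposed, and the indicator is itself defined by change from baseline, so it has no pre-intervention value to supply the contrast. The only comparator is a single constant applied to everyone.

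The term that can be fitted therefore mixes two things: a different response to the programme, and a different chance of reaching two goals without it. The plan accepts in general that the chance of meeting a goal depends on where a participant starts: in Data Collection it says that someone with a baseline HbA1c of 5.8% "is unlikely to reduce this risk factor by 0.5" percentage points.

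At stake is what the trial may say about who benefits. A significant result, read beside the plan's caution that only large modification is detectable, could be taken as strong evidence that the programme works better in one group, when the groups differ only in background success.

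**Working it through.** The plan gives no figure for this analysis, so there is none to reproduce. Its 93% power statement concerns the overall comparison of 33% with 21% and is not in dispute here. No intraclass correlation (ICC) is stated for that endpoint; with 1,600/(1 + 199 × ICC) effective participants, 93% corresponds to an ICC of about 0.047 (two-sided, normal approximation).

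**Inputs from the documents**
- One arm, so the intervention indicator I = 1 for all (Approach).
- Benchmark 21%, target 33% (Aim 2; Sample Size Selection). Ratio 33/21 = 1.571; difference 12 points.
- Analysed: 8 sites × 250 × 0.80 = 1,600, or 200 per site.
- Significance level 0.05; sidedness is not stated, two-sided assumed.

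**Assumed, because the documents are silent:** stratum background rates, ICC of 0 to 0.05, and equal halves unless noted.

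**1. Identifiability.** Write log p = b0 + b1·I + b2·M + b3·(M×I). With I = 1 for everyone this is (b0 + b1) + (b2 + b3)·M. The four columns have rank 2; without the I column, the remaining three also have rank 2. A concurrent comparator would give rank 4 of 4. Here b2 is the modifier's association with background success and b3 is effect modification. Only their sum can be estimated, and it equals b3 only if b2 = 0. Any common background rate would satisfy that for the test; 21% is the common rate the plan assumes.

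**2. Stratified estimates.** Apparent ratio = background × true ratio / 0.21. With the same true ratio of 1.571 in both halves:

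| Background | Success on programme | Apparent ratio | Score-test rejection |
|---|---|---|---|
| 21% / 21% | 33.0% / 33.0% | 1.57 / 1.57 | 2–4% |
| 19% / 23% | 29.9% / 36.1% | 1.42 / 1.72 | 54–62% |
| 18% / 24% | 28.3% / 37.7% | 1.35 / 1.80 | 86–92% |
| 16% / 26% | 25.1% / 40.9% | 1.20 / 1.95 | about 100% |

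The last column comes from 300 simulated trials per setting (8 × 200, exchangeable GEE, log link, robust score test), with the range taken over ICC 0, 0.02 and 0.05. The Monte Carlo standard error is about √(0.9 × 0.1/300) = 1.7 points at 90%. The benchmark enters as an offset log(0.21), so that the exponentiated intercept is a ratio to 21%, and the working variance is Poisson; the plan subtracts 21% from the indicator and specifies binomial variance. Step 1 does not depend on that choice.

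For comparison, treating participants as independent at 18%/24%: z = 0.094/√[(0.283 × 0.717 + 0.377 × 0.623)/800] = 0.094/0.0234 = 4.0, or about 98% rejection. The clustered score test gives less.

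**3. Unequal subgroups.** A 27:73 split is close to the share of women at several sites in Table 1. Holding the overall background at 21%, the larger group has (21 − 0.27 × 19)/0.73 = 21.7% or (21 − 0.27 × 18)/0.73 = 22.1%. Independence-based rejection is 36% at 19%/21.7% and 66% at 18%/22.1%, against 76% and 98% for 19%/23% and 18%/24% in equal halves by the same method. Part of that drop reflects the smaller background gap.

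**4. Difference scale.** If the programme adds 12 points in both halves, 18% and 24% become 30% and 36%. Against 21% the apparent effects are 9 and 15 points.

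**5. Masking.** With backgrounds of 18% and 24% and true ratios of 0.33/0.18 = 1.83 and 0.33/0.24 = 1.375, both halves show 33% and an apparent ratio of 1.57. Real modification disappears.

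**6. Outcomes with a baseline value.** In a pre/post layout the columns for constant, time, modifier and time × modifier have rank 4 of 4, so that contrast is estimable.

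**The case against.** The strongest reply is that no false signal is inevitable. The documents give no background rates by stratum, and with equal rates the score test behaves properly (2–4%). This stands: a reader might infer that the plan *will* report modification that is not there, but the documents support only that it can.

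Nor does the HbA1c example show otherwise. It concerns baseline HbA1c, which is not among the modifiers named, and the same sentence notes that such a person may still succeed on triglycerides or blood pressure. It shows that background success can depend on starting risk, not that it differs by gender or age.

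A reader might also extend the point to Aim 1, which plans to examine "heterogeneity in the intervention effect over time on each outcome by education, income, gender, age" and other characteristics, and to the continuous Aim 2 endpoints. That does not follow. Those outcomes are analysed as repeated measures or within-person change, no 21% enters, and the modifier contrast on change is estimable. What remains there is the general limitation of uncontrolled pre-post data, which is a different point.

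The consequences should not be inflated either. The plan treats the analysis as secondary, and no section ties these tests to targeting; the sustainability section speaks only of using trial results in general to tailor the programme.

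Two possible rescues fail. The Preliminary data section says that D-CLIP effects were consistent across subgroups, but that describes effects, not control rates. The CARRS comparator in the future-plans section is an additional analysis that needs separate funding and is not linked to this test.

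**Conclusion.** The point holds for the primary endpoint and for any other endpoint compared with one fixed external rate. There the specified cross-product is not identifiable. The test that can be fitted compares success rates between subgroups, and it measures effect modification only under an unstated assumption of common background success. That conclusion follows from the design and needs no numerical assumption.

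The size depends on background rates that the documents do not give. A six-point gap (18%/24%) with one true ratio of 1.57 gives apparent ratios of 1.35 and 1.80 and rejection of about 86–92% in equal halves; a four-point gap gives 54–62%; no gap gives 2–4%. Unequal subgroups lower these figures. Differences in background can equally hide real modification. The overall comparison with 21% is unaffected, and so are analyses of change in continuous and Aim 1 outcomes.

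**What to change.** For endpoints compared with a fixed external rate, rename the analysis *differences in response between subgroups*, report the success rate in each stratum, test the modifier coefficient, and remove the effect-modification test and claim. State separately that for continuous and repeated-measures outcomes the contrast is time × modifier (or the modifier's coefficient on change). This costs a few lines of SAP wording and no data.

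As an optional sensitivity analysis, replace the single 21% by D-CLIP control percentages within each stratum and carry their sampling error. Limit this to participants with prediabetes, because D-CLIP enrolled only such people while Sample Size Selection puts them at two thirds here, and note that the 21% is reported among 18-month results whereas this endpoint is at three years. The price is wide intervals. Assuming about 301 D-CLIP controls (half of 602; the arm size is not given), each half has about 150. The standard error of a stratum benchmark is √(0.21 × 0.79/150) = 3.3 points, and that of the difference between two is √2 × 3.3 = 4.7 points, not far below the six-point gap in the illustration. Relabelling is therefore the main remedy.
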